4.6.5 Vital Signs

4.6.5.1 Definitions and Derivations

The following vital signs will be measured:

- Body weight (kg)
- Body temperature (degrees Celsius)
- Heart (pulse) rate (bpm)
- Respiratory rate (1/min)
- Oxygen saturation (SpO₂)
- Systolic blood pressure (SBP) (mmHg)
- Diastolic blood pressure (DBP) (mmHg)

Vital signs will be collected at the visits indicated in the SoA (see CSP).

Additionally, vital signs values will be classified as normal (if value is within normal reference range), low (if value is below the normal reference range or limit), and high (if value is above the normal reference range or limit) according to the normal reference values given in [Table 11](#) below. Based on the categories presented in [Table 11](#) variables may have 2-level classification and 3-level classification.

Systolic and diastolic blood pressure will be measured in triplicates and the mean of the three measurements will be collected in the EDC and used in the subsequent analyses.

Table 11 - Vital Signs Normal Reference Ranges

Parameter	Normal reference range
Systolic blood pressure	< 140 mmHg
Diastolic blood pressure	< 90 mmHg
Heart (pulse) rate	50-100 bpm
Body temperature	≤ 37°C
Oxygen saturation	≥ 95%
Respiratory rate	12-20 per minute

Abnormalities in Vital Signs

Treatment emergent abnormalities are defined as abnormalities that manifested after the first administration of study treatment.

The presence of the abnormalities will be determined based on the following criteria (at any time during treatment/study, as applicable):

1. Systolic blood pressure
 - a. Maximum value is > 40 mmHg increase from baseline
 - b. Maximum value is > 180 mmHg
 - c. Maximum value is ≥ 140 mmHg with ≥ 20 mmHg increase from baseline
 - d. Maximum value is ≥ 160 mmHg with ≥ 30 mmHg increase from baseline
 - e. Maximum value is ≥ 180 mmHg with ≥ 40 mmHg increase from baseline
 - f. For change from baseline to mean value
 - i. > 10 mmHg
 - ii. > 20 mmHg
 - iii. > 30 mmHg
 - iv. > 40 mmHg
2. Diastolic blood pressure
 - a. Maximum value is > 20 mmHg increase from baseline
 - b. Maximum value is > 100 mmHg
 - c. Maximum value is ≥ 90 mmHg with ≥ 10 mmHg increase from baseline
 - d. Maximum value is ≥ 100 mmHg with ≥ 20 mmHg increase from baseline
 - e. For change from baseline to mean value
 - i. > 10 mmHg
 - ii. > 20 mmHg
 - iii. > 30 mmHg
 - iv. > 40 mmHg
3. Heart rate

- a. Maximum value is > 100 beats/min with > 20 beats/min increase from baseline
- b. Minimum value is < 50 beats/min with > 20 beats/min decrease from baseline
- c. Minimum value is < 60 beats/min with > 20 beats/min decrease from baseline

Shift Tables

Shift tables will be presented for all parameters based on the following thresholds:

1. Diastolic Blood Pressure (DBP):

- Normal (< 90 mmHg)
- High (≥ 90 mmHg)

2. Systolic Blood Pressure (SBP):

- Normal (< 140 mmHg)
- High (≥ 140 mmHg)

3. Heart (Pulse) Rate:

- Low (< 50 bpm)
- Normal (50-100 bpm)
- High (> 100 bpm)

4. Body Temperature:

- Normal ($\leq 37^{\circ}\text{C}$)
- High ($> 37^{\circ}\text{C}$)

5. Oxygen Saturation:

- Low ($< 95\%$)
- Normal ($\geq 95\%$)

6. Respiratory Rate:

- Low (<12 breaths/min)
- Normal (12-20 breaths/min)
- High (>20 breaths/min)

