### **Medical Conditions**

- 1 Estimated glomerular filtration rate (eGFR) < 45 mL/min/1.73m^2 using the Chronic Kidney Disease-Epidemiology Collaboration (CKD-Epi 2021(Age, Sex)) equation at Visit 1.
- 2 History or presence of gastrointestinal, hepatic or renal disease or any other conditions known to interfere with absorption, distribution, metabolism, or excretion of drugs.
- 3 Any uncontrolled or serious disease, or any medical (eg, known major active infection or major hematological, renal, metabolic, gastrointestinal, respiratory, or endocrine dysfunction) or surgical condition that, in the opinion of the investigator, may either interfere with participation in the clinical study and/or put the participant at significant risk.
- 4 Poorly controlled type 2 diabetes mellitus, defined as HbA1c > 10% at Visit 1.
- 5 Acute ischemic cardiovascular event in the last 12 months prior to randomization however patients can be included if it is > 6 months from coronary artery bypass graft surgery (CABG) surgery and > 3 months after percutaneous coronary intervention (PCI).
- 6 Heart failure with New York Heart Association (NYHA) Class III-IV.
- 7 Malignancy (except non-melanoma skin cancers, cervical in-situ carcinoma, breast ductal carcinoma in-situ, or Stage 1 prostate carcinoma) within the last 10 years.
- 8 Recipient of any major organ transplant, eg, lung, liver, heart, bone marrow, renal.
- 9 LDL or plasma apheresis within 12 months prior to randomization.
- 10 Uncontrolled hypertension defined as average sitting SBP > 160 mmHg or DBP > 90 mmHg at Visit 1. It is recommended that antihypertensive treatment should be considered/initiated at the PI's discretion and in accordance with applicable clinical guidelines in order to optimize blood pressure for participants with hypertension during the clinical study.
- 11 Heart rate after 10 minutes supine rest < 50 bpm or > 100 bpm at Visit 1.
- 12 Any laboratory values with the following deviations at Screening Visit 1; test may be repeated at the discretion of the investigator if abnormal:
  - (a) Any positive result on screening for hepatitis B, hepatitis C or HIV.

- (b) ALT > 1.5 × ULN
- (c) AST > 1.5 × ULN
- (d) TBL > ULN
- (e) Hemoglobin < 12 g/dL in men or < 11 g/dL in women
- (f) Potassium < LLN

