### **7.1.2 Cardiac Stopping Criteria**

Discontinuation of study intervention for abnormal cardiac tests is required by the investigator when a participant meets one of the conditions outlined below:

- Average absolute (regardless of baseline value) cardiac QTc interval corrected for heart rate by QTcF  $> 500$  msec, or an increase of QTcF  $> 60$  msec above the baseline value, confirmed (persistent for  $\geq 5$  minutes) on repeat triplicate 12-lead ECGs.

Any one of the following:

- Tachycardia, defined as resting supine pulse rate  $> 125$  beats per minute persisting for at least 10 minutes.
- Symptomatic bradycardia, defined as resting supine pulse rate  $< 40$  beats per minute while awake, persisting for at least 10 minutes.
- Asymptomatic bradycardia, defined as resting supine pulse rate  $< 30$  beats per minute while awake persisting for at least 10 minutes.
- Hypertension, defined as an increase from baseline in resting supine systolic  $> 40$  mmHg or above 180 mmHg and persisting for at least 10 minutes and/or increase from baseline in resting supine diastolic BP  $> 20$  mmHg or above 100 mmHg and persisting for at least 10 minutes.

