The predefined criteria for a parameter abnormality are based on reference ranges from the central lab and defined as $>\text{ULN}$ or $<\text{LLN}$, where applicable. In addition, the following definitions of abnormalities (non-mutually exclusive) will be used for specific parameters listed below:

- Platelet count: < 50 , < 75 , < 100 , $< 150 \times 10^9/\text{L}$, and $> 30\%$ decrease from baseline
- ALT: $> 1 \times \text{ULN}$, $> 3 \times \text{ULN}$, $> 5 \times \text{ULN}$, $> 10 \times \text{ULN}$, $> 20 \times \text{ULN}$
- AST: $> 1 \times \text{ULN}$, $> 3 \times \text{ULN}$, $> 5 \times \text{ULN}$, $> 10 \times \text{ULN}$, $> 20 \times \text{ULN}$
- ALP: $> 2 \times \text{ULN}$, $> 3 \times \text{ULN}$
- Total Bilirubin (TBL): $> 2 \times \text{ULN}$, $> 5 \times \text{ULN}$, $> 8 \times \text{ULN}$
- eGFR: $\geq 25\%$ decrease, $\geq 50\%$ decrease and $\geq 75\%$ decrease
- Creatinine: $\geq 1.5 \times \text{baseline}$, $\geq 2 \times \text{baseline}$ and $\geq 3 \times \text{baseline}$

Potential Hy's Law

Potential Hy's law is defined as AST or ALT $\geq 3 \times \text{ULN}$ together with TBL $\geq 2 \times \text{ULN}$ at any point during the study, following the start of study intervention irrespective of an increase in ALP. The elevation in transaminases must precede or be coincident with (i.e., on the same day) the elevation in TBL, but there is no specified timeframe within which the elevations in transaminases and TBL must occur.

Shift Tables

Shift tables will be presented for the following parameters according to unique thresholds:

For ALT and AST:

- $\leq 1 \times \text{ULN}$
- $> 1 \times \text{ULN}$ and $\leq 3 \times \text{ULN}$
- $> 3 \times \text{ULN}$ and $\leq 5 \times \text{ULN}$
- $> 5 \times \text{ULN}$ and $\leq 10 \times \text{ULN}$
- $> 10 \times \text{ULN}$ and $\leq 20 \times \text{ULN}$
- $> 20 \times \text{ULN}$

Bilirubin, total will be categorised into:

- $\leq 2 \times \text{ULN}$
- $> 2 \times \text{ULN}$ and $\leq 5 \times \text{ULN}$
- $> 5 \times \text{ULN}$ and $\leq 8 \times \text{ULN}$
- $> 8 \times \text{ULN}$

ALP will be categorised into:

- $\leq 2 \times \text{ULN}$
- $> 2 \times \text{ULN}$ and $\leq 3 \times \text{ULN}$
- $> 3 \times \text{ULN}$

Platelet absolute count will be categorised into:

- $< 50 \times 10^9/\text{L}$
- $\geq 50 \times 10^9/\text{L}$ and $< 75 \times 10^9/\text{L}$
- $\geq 75 \times 10^9/\text{L}$ and $< 100 \times 10^9/\text{L}$

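### All three SAP heart-rate abnormality criteria require a change of more than 20 bpm, so a participant with a baseline of 50 to just under 60 bpm can record a pulse of 30–39 bpm and not be counted in the treatment-emergent vital-signs table

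*SAP*

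**What the plan says.** SAP 4.6.5.1 makes its list decisive: "The presence of the abnormalities will be determined based on the following criteria (at any time during treatment/study, as applicable"). For heart rate the list has three entries:

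- 3a: "Maximum value is > 100 beats/min with > 20 beats/min increase from baseline"
- 3b: "Minimum value is < 50 beats/min with > 20 beats/min decrease from baseline"
- 3c: "Minimum value is < 60 beats/min with > 20 beats/min decrease from baseline"

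Each joins a level to a change; none is a level alone. SAP 4.6.5.2 uses these definitions for the treatment-emergent vital-signs summary, the risk differences against placebo with 95% confidence intervals, and the listing of key subject information.

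Blood pressure is treated differently in the same list. Systolic pressure has a change-only entry, "Maximum value is > 40 mmHg increase from baseline", and a level-only entry above 180 mmHg. Diastolic pressure has the matching pair at 20 and 100 mmHg. SAP 4.6.6.1 does the same for QTcF, at 500 ms and a 60 ms increase. All of these are the figures in Protocol 7.1.2.

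Protocol 7.1.2 also gives pulse figures. One entry begins "Symptomatic bradycardia, defined as resting supine pulse rate" and sets the figure at below 40 bpm, awake, lasting 10 minutes or more. The asymptomatic figure is below 30 bpm and the tachycardia figure above 125 bpm. Protocol 5.2 exclusion 11 reads "Heart rate after 10 minutes supine rest < 50 bpm or > 100 bpm at Visit 1", so a pulse of 50 bpm is eligible.

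**The concern.** The change condition bears hardest on participants who start with a low pulse. They have the least distance to fall before reaching a markedly low value, yet they must still fall by more than 20 bpm to be counted. The table that compares arms could then show nothing for a participant recorded at 36 bpm.

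This matters because Protocol 9.2 says the sample size is driven by safety and tolerability. Safety is not formally tested, and for vital signs the risk differences against placebo are the planned between-arm comparison.

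Pulse is also the exception. For blood pressure and QTcF the SAP provides rows that need no second condition, at the same values the protocol uses for stopping.

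**Working it through.** The plan states no figure to reproduce; the check is on thresholds.

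**Inputs.** Criteria 3a–3c (SAP 4.6.5.1); baseline as the last pre-dose value (SAP 3.3.1.2); lowest eligible pulse 50 bpm at Visit 1 (Protocol 5.2, exclusion 11); pulse figures of 40, 30 and 125 bpm (Protocol 7.1.2); pulse recorded as the average of three readings (Protocol 8.2.2).

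**Step 1: when a low pulse is counted.** Let b be baseline and m the minimum. 3b needs m < 50 and b − m > 20; 3c needs m < 60 and b − m > 20. Anything meeting 3b also meets 3c, so a low pulse is counted only if m < min(60, b − 20).

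**Step 2: values below 40 bpm.** Here the binding condition is m < b − 20. A value is uncounted when b − 20 ≤ m < 40, which is possible only if b < 60.

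| Baseline b | Counted only if m is below | Uncounted values below 40 (whole bpm) | How many |
|---|---|---|---|
| 50 | 30 | 30–39 | 10 |
| 52 | 32 | 32–39 | 8 |
| 55 | 35 | 35–39 | 5 |
| 58 | 38 | 38–39 | 2 |
| 59 | 39 | 39 | 1 |
| 60 | 40 | none | 0 |

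**Step 3: extent of the gap.** For each whole-bpm baseline from 50 to 59 the number of uncounted values is 60 − b. The total is 10 + 9 + … + 1 = 55 combinations. Because pulse is an average of three readings, values in thirds are possible, and the highest affected baseline is then 59⅔. These combinations map the gap; they are not numbers of participants.

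**Step 4: two cases side by side.** From 55 to 36 the fall is 19, which is not more than 20, so none of 3a–3c is met. From 80 to 59 the fall is 21 and 59 is below 60, so 3c is met, although SAP Table 11 classes 59 bpm as normal (50–100).

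**Step 5: the other two pulse figures.** With b ≥ 50 and m < 30, the fall exceeds 20, so 3b and 3c are met. With b ≤ 100 and a maximum above 125, the rise exceeds 25, so 3a is met. For baselines of 50–100 nothing is missed at either figure.

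**Step 6: comparison with blood pressure.** Exclusion 10 allows entry up to 160/90 mmHg. A rise from 160 to 181 mmHg systolic (21 mmHg) or from 90 to 101 mmHg diastolic (11 mmHg) is counted by the level-only rows, whatever the change. No value above 180 or 100 mmHg can escape.

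**Step 7: effect of one added row.** With a level-only row at m < 40, an uncounted value would have to be both below 40 and at least 40. The 55 combinations become 0.

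**The case against.** The strongest reply is that such a case remains visible elsewhere. The shift table to the minimum needs no 20 bpm change and would show Normal to Low. Observed pulse is summarised by arm and visit with the minimum, and individual vital signs are listed. Under Protocol 8.3.4, a deterioration that is the reason for stopping study treatment is an adverse event, and SAP 4.6.2.2 tabulates adverse events leading to discontinuation by arm. All of this stands, and it is why the point is minor. But the shift table's only low class is below 50 bpm, so 36 and 49 look alike. A visit minimum shows the lowest value but not how many participants were that low. Listings give no comparison. Adverse-event tables count terms, not pulse levels, and SAP 4.6.2 plans no risk difference for them. ECG heart rate is summarised too, but the numeric ECG criteria in SAP 4.6.6.1 cover QTcF only.

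A second reply is that nothing requires abnormality criteria to mirror stopping rules, and that Protocol Table 2 names QT prolongation and blood pressure elevation as risks but not bradycardia. That also stands: this is a reporting gap, not a contradiction between the documents.

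Three stronger readings are tempting and are not supported:

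- *That participants who met the protocol's stopping rule go uncounted.* The 40 bpm rule needs symptoms and a supine pulse persisting for at least 10 minutes. Scheduled vital signs are taken seated (Protocol 8.2.2), so a recorded 36 bpm does not by itself meet it.
- *That values below 30 or above 125 bpm are lost too.* Step 5 shows they are already counted for baselines of 50–100.
- *That ALT or AST above 8 × ULN, a protocol stopping value, is lost in the same way because the SAP goes from 5 to 10 × ULN.* SAP 4.6.3.1 says "the following definitions of abnormalities (non-mutually exclusive) will be used for specific parameters listed below", so any such value is counted in the row above 5 × ULN. A cut at 8 would only be finer.

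**Conclusion.** The point holds in a narrow form. With a baseline of 50 to just under 60 bpm, a minimum of 30–39 bpm that is no more than 20 below baseline is not counted in the treatment-emergent vital-signs table, its risk differences or its key-subject listing. No other planned output gives a per-arm count or risk difference below 40 bpm.

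The size can be stated only as a range of values (55 whole-bpm combinations). The documents give neither a baseline pulse distribution nor a rate of falls to 30–39 bpm, so the number of participants affected cannot be derived and may be zero.

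The lower end of 50 bpm assumes that the analysis baseline respects the Visit 1 entry limit. That limit is a supine value, while baseline is the last pre-dose value, normally the seated Day 1 reading, so a baseline below 50 is possible. The gap is then wider: 49 to 29 is a fall of exactly 20 and is missed.

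Severity: minor; a cheap improvement to the safety comparison.

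**What to change.** In SAP 4.6.5.1 item 3, keep 3a–3c and add one criterion with no baseline condition, at a figure the protocol already uses: minimum value below 40 beats/min. Carry it into the same frequency table, risk differences and key-subject listing under 4.6.5.2. It would also capture values below 30 bpm from a baseline under 50. Rows at below 30 or above 125 bpm, or at ALT/AST above 8 × ULN, are not needed on this argument.

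A footnote should say that the row counts recorded readings and not met stopping rules, since posture, symptoms and persistence differ. The change concerns reporting only; it alters no stopping rule and takes no view on which clinical limit is right.

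The cost is a line of SAP text and one table row from data already collected, with no change to conduct. The downside is one more descriptive comparison without multiplicity control.

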4.6.5.2 Presentations

Observed values and change from baseline in vital signs will be summarised by the treatment group and visit with descriptive statistics.

A figure with mean change from baseline over time by treatment group will be presented.

Shift tables from baseline to maximum on-treatment and on-study value (excluding Oxygen Saturation, because shift to maximum is not relevant), from baseline to minimum on-treatment and on-study value will be presented for each treatment group and AZD0780 Total.

Treatment emergent vital signs abnormalities will be reported as defined in Section 4.6.5.1.

Risk differences between active treatment groups and Placebo will be presented, alongside 95% confidence intervals of the risk difference according to the definitions in Section 4.6.3.1.

The key subject information about the treatment emergent vital signs abnormalities will also be listed. Additionally, individual vital signs data will be listed.

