**Table 2 Risk Assessment of AZD0780**

Potential risk of clinical significance	Summary of data/rationale for risk	Mitigation strategy
QT-prolongation	
In an in vitro assay, AZD0780 was shown to be an inhibitor of the hERG channel (human ether-a-go-go-related gene). hERG channel inhibition can cause QT-prolongation and potentially cardiac arrhythmia, including Torsade de Pointes. Based on the in vitro data, modeling predicted a high likelihood of QT-prolongation at free plasma levels of AZD0780 at doses to be investigated in AZD0780 clinical studies.
 
In the cardiovascular safety studies and the 1 month toxicology study of AZD0780 in cynomolgus monkeys, although QT-prolongation was observed, the pre-clinical data were consistent with a reversible mode of hERG channel inhibition and QT-prolongation. There were no observations of AZD0780 related arrhythmias in the in vivo studies at the dose levels tested.
 
No ECG findings of safety concern have been identified in the ongoing phase 1 clinical study (Study D7960C00001) at single doses of up to [REDACTED] mg or repeated doses up to [REDACTED] mg once daily.
	
 
Exclusion of participants with clinically important abnormalities in rhythm, conduction or morphology of the resting ECG and any clinically important abnormalities in the 12 lead ECG; QTcF > 450 ms; AV-block grade II-III; sinus node dysfunction with significant sinus pause untreated with pacemaker; and cardiac tachyarrhythmias (exclusion criteria 13-14).
 
Regular ECG recordings and assessment.
 
Individual stopping criteria have been defined to consider QTc and QTcF values outside pre-specified ranges.
 

Blood pressure elevation	
In the cardiovascular safety studies of AZD0780 in cynomolgus monkeys, a transient increase in arterial BP was observed between 0.5h – 8h post dose at the highest tested dose of [REDACTED] mg/kg (free Cmax of [REDACTED] µmol/L).
	
 
Only participants within a defined range of BP will be included in the study (exclusion criterion 10).
 
It is recommended that antihypertensive treatment is considered/initiated at the PI's discretion and in accordance with applicable clinical guidelines in order to optimize blood pressure for participants with hypertension during the clinical study. BP will be monitored throughout the study.
 

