Potential risk of clinical significance	Summary of data/rationale for risk	Mitigation strategy
Dyspnea	
In in vitro studies, AZD0780 is an adenosine transport inhibitor (IC50 ~15 <math>\mu</math>M). Inhibition of adenosine transporters can result in dyspnea and bronchospasm in patients with respiratory disease. In addition, inhibition of <math>\alpha</math>1A adrenoceptors (Ki=18 <math>\mu</math>M and functional IC50 ~47 <math>\mu</math>M) identified in AZD0780 in vitro studies, can result in dyspnea, observed in clinical trials with <math>\alpha</math>-adrenoceptor antagonists.
 
The respiratory safety pharmacology study with AZD0780 in rats did not show any effect on respiratory parameters as assessed by plethysmography.
	
 
Exclusion of participants with any uncontrolled or serious disease, or any medical (eg, known major active infection or major hematological, renal, metabolic, gastrointestinal, respiratory, or endocrine dysfunction) or surgical condition that, in the opinion of the investigator, may either interfere with participation in the clinical study and/or put the participant at significant risk (exclusion criterion 3).
 
Adverse events, physical examinations and vital signs, including respiratory rate and pulse oximetry, will be monitored throughout the study.
 
Individual stopping criteria have been defined to consider exacerbation of respiratory disease.
 

Effects on Reproduction	
AZD0780 was shown to be an antagonist of the serotonin receptor 5-hydroxytryptamine receptor 2B (5-HT2B). Possible adverse effects of 5-HT2B receptor antagonism include developmental toxicity (based on complete knockout).
 
AZD0780 inhibits <math>\alpha</math>1A adrenoceptor. In clinical studies <math>\alpha</math>1A adrenoceptor antagonism has resulted in a reduction of uterine and vas deferens contractility and AE reports of abnormal ejaculation.
 
Nonclinical developmental toxicity studies for AZD0780 have not yet been performed.
	
 
Women of childbearing potential will be excluded from the study (inclusion criteria 1 and 8).
 
Reproductive restrictions will be in place throughout the study.
 

Potential risk of clinical significance	Summary of data/rationale for risk	Mitigation strategy

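### The planned shift to minimum blood pressure has no Low category, and no blood pressure abnormality criterion looks downward: a minor safety-reporting gap

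*SAP*

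**What the plan says.** SAP 4.6.5.1 (Table 11 and the shift-table categories) gives SBP the levels "Normal (< 140 mmHg") and "High (≥ 140 mmHg"). DBP has "Normal (< 90 mmHg") and a High level from 90 mmHg. The general rule assigns a value as "low (if value is below the normal reference range or limit"), and the section notes that "variables may have 2-level classification and 3-level classification". Since blood pressure has only an upper limit, no value can be classed as low.

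The treatment-emergent list in the same section covers SBP (items a to f), DBP (items a to e) and heart rate (items a to c). SAP 4.6.5.2 plans risk differences against placebo with 95% confidence intervals for these abnormalities. It also plans shifts to the maximum, with oxygen saturation left out as not relevant in that direction, and shifts "from baseline to minimum on-treatment and on-study value will be presented for each treatment group and AZD0780 Total", from which no parameter is left out.

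For the dyspnea risk, Table 2 of the protocol states: "Adverse events, physical examinations and vital signs, including respiratory rate and pulse oximetry, will be monitored throughout the study". For the risk of blood pressure elevation it says: "It is recommended that antihypertensive treatment is considered/initiated at the PI's discretion".

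**The concern.** A shift to the minimum value is normally produced to show how many participants dropped into a low category. For blood pressure there is no such category, so a participant with a very low reading is tabulated under the label Normal. The abnormality criteria do not fill the gap because none is triggered by a fall. A reader of the safety tables could take the Normal-to-Normal counts as reassurance about low readings when the table has not examined them.

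Protocol 9.2 says the sample size is driven by safety and tolerability. The SAP's between-arm estimate for vital-sign abnormalities is the risk difference, and low blood pressure receives none. SpO2 and respiratory rate, on which the protocol relies for a risk it does name, also receive none because they are absent from the treatment-emergent list.

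**Working it through.** There is no stated figure to reproduce. The check applies the categories and criteria as written.

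**Step 1: the rules side by side** (SAP 4.6.5.1 and 4.6.5.2)

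| Parameter | Shift levels | Low level | In shift to minimum | Downward treatment-emergent items |
|---|---|---|---|---|
| SBP | <140, ≥140 mmHg | no | yes | 0 of 6 |
| DBP | <90, ≥90 mmHg | no | yes | 0 of 5 |
| Heart rate | <50, 50–100, >100 bpm | yes | yes | 2 of 3 |
| SpO2 | <95%, ≥95% | yes | yes | no items listed |
| Respiratory rate | <12, 12–20, >20 per min | yes | yes | no items listed |
| Temperature | ≤37, >37 °C | no | yes | no items listed |

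**Step 2: what the minimum table can show for SBP.** It has four cells.
- High to Normal: at least one later value below 140. This does register a fall.
- High to High: never below 140.
- Normal to High: lowest later value at least 140, a sustained rise.
- Normal to Normal: everyone else. Minima of 60, 80, 89, 120 and 139 all fall here if baseline was below 140.

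DBP behaves the same way around 90: 35, 50, 59 and 89 are all Normal.

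**Step 3: the abnormality criteria under a fall.** Let B be baseline, M the maximum and A the mean of later values. Suppose every later value is at or below B.
- Then M − B ≤ 0, so SBP a, c, d, e and DBP a, c, d cannot be met.
- A − B ≤ 0, so SBP f and DBP e (change above 10, 20, 30 or 40 mmHg) cannot be met.
- SBP b needs a value above 180 and DBP b one above 100. In a falling profile that requires a baseline above those values, whereas protocol exclusion criterion 10 bars SBP above 160 or DBP above 90 at Visit 1. Even if met, item b flags the high value, not the fall.

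**Step 4: worked example.** The profiles are assumed, with one value for each of the six post-baseline visits.
- SBP: B = 125; later values 120, 110, 78, 85, 90, 95. M − B = 120 − 125 = −5. A = 578/6 = 96.3, so A − B = −28.7. No item is met; the shift is Normal to Normal.
- DBP: B = 78; later values 75, 70, 42, 50, 55, 60. M − B = −3. A = 352/6 = 58.7, so A − B = −19.3. No item is met; the shift is Normal to Normal.

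**Step 5: could SBP f and DBP e mean absolute change?** If so, the SBP example would meet the 10 and 20 mmHg thresholds and the DBP example the 10 mmHg threshold. The text does not say this. SAP 4.6.3.1 defines change for laboratory values as post-baseline minus baseline, and the heart rate items name a decrease when one is meant.

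**The case against.** The strongest reply is that the upward focus is deliberate. Table 2 of the protocol lists blood pressure elevation only, protocol 7.1.2 has only a hypertension stopping criterion for blood pressure, and SAP items 1a, 1b, 2a and 2b use its thresholds (rise above 40 or value above 180 systolic; rise above 20 or value above 100 diastolic). The SAP openly allows two-level classification. This stands, and it limits the weight of the point. It does not explain why a minimum shift was planned for blood pressure.

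Three stronger readings are tempting, and the documents do not support them.
- *The minimum table is empty.* It is not. High to Normal shows a fall, and High to High shows sustained elevation.
- *Low blood pressure would be hidden.* It would not. SAP 3.3.1 includes quartiles, minimum and maximum in the descriptive statistics, and 4.6.5.2 applies these to observed values and change by visit and arm. Individual values are listed. Protocol 8.3.4 has clinically relevant deterioration in vital signs reported as adverse events, which SAP 4.6.2.2 counts by arm. However, by-visit summaries use only data mapped to scheduled windows, and adverse event reporting depends on the investigator's judgement. Neither counts participants below a measured value.
- *The protocol itself points to hypotension.* Table 2 links alpha-1A adrenoceptor inhibition to dyspnea and reproductive effects. The recommendation on antihypertensive treatment is a mitigation for elevation in participants with hypertension. A fall is possible when such treatment is started, but hypotension is nowhere listed as a risk.

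On SpO2 and respiratory rate, the reply is that shift counts by arm at the Table 11 limits are already planned. That is correct: only the risk difference and its interval are missing.

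**Conclusion.** The point holds as a minor safety-reporting gap. Followed exactly, the SAP labels any SBP below 140 and any DBP below 90 as Normal in a table built on the minimum value. None of its 11 blood pressure items responds to a fall. No planned output gives a participant count based on measured low blood pressure, or a risk difference against placebo. For SpO2 and respiratory rate the gap is narrower: counts exist, but risk differences do not.

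The conclusion rests on reading SBP f and DBP e as increases, which is their plain sense. The documents give no rate of low readings, so the number of participants affected cannot be estimated. Efficacy, alpha and sample size are untouched, and the text does not support a claim that a hypotension signal would be missed altogether.

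**What to change.** Amend SAP 4.6.5.1, Table 11 and the table shells before unblinding.

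1. Add a Low reporting level for SBP and DBP and use it in the shift to minimum. The sponsor chooses the cut-offs, through staff who have seen no unblinded interim results.
2. Add treatment-emergent items that combine a minimum value with a decrease from baseline, as heart rate already has, so that low blood pressure receives counts and risk differences.
3. Failing 1 and 2, exempt blood pressure from the shift to minimum and state why, as was done for the SpO2 shift to maximum. Body temperature has the same two-level structure and needs the same choice.
4. Add SpO2 below 95% and respiratory rate below 12 or above 20, the limits implied by Table 11, to the treatment-emergent list so that they receive risk differences.
5. State that SBP f and DBP e refer to increases.

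The cost is wording and a few more table rows. Vital signs are already collected at every visit. These are reporting categories only and change no participant management.
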